### **Patient disposition**

Subject disposition will be summarized using the FAS by cohorts.

A summary of patient status and reason for end of study will be provided. This display will show the number and percentage of patients who withdrew from the study, and primary reasons for study withdrawal. Reasons for study withdrawal will be presented in the order they are displayed in the eCRF.

A summary of study treatment status will be provided. This display will show the number and percentage of patients who discontinued study treatment or has treatment ongoing or completed the study and a summary of the primary reasons for discontinuation of study treatment. Reasons for study treatment discontinuation will be presented in the order they are displayed in the eCRF. A listing of study treatment discontinuation will be generated. The listing will include last dose date, and reasons for study treatment discontinuation.

### **Analysis sets**

The number and percentages (based on the total number of FAS patients) of patients in each analysis set (defined in Section 2.2) will be summarized.

## **2.4 Treatments (study treatment, rescue medication, concomitant therapies, compliance)**

### **2.4.1 Study treatment / compliance**

Dose administration data will be summarized by cohorts and by pre-craniotomy phase and post-craniotomy phase using the Safety Set.

In addition, a listing of exposure to dabrafenib, dabrafenib and trametinib will be produced.

### **Duration of exposure to study treatment**

Duration of exposure to study treatment is considered by taking into account the duration of exposure to the investigational drugs:

Duration of exposure to study treatment (days) = (last date of exposure to study treatment) – (date of first administration of study treatment) + 1.

The last date of exposure to study treatment is the latest of the last dates of exposure to investigational drug.

Summary of duration of exposure of study treatment in appropriate time units will include categorical summaries based on intervals and continuous summaries (i.e. mean, standard deviation etc.) using appropriate units of time.

## **2.4.2 Prior, concomitant and post therapies**

Not applicable.

## **2.5 Analysis of the primary objective**

### **2.5.1 Primary endpoint**

As a short close-out CSR will be produced, summary analyses will not be performed. The concentration and distribution (when applicable) of dabrafenib, dabrafenib metabolites and trametinib (Cohort B only) will be listed for each cohort by tissue type (i.e., parenchymal brain metastases, optional assessment of extracranial metastases, plasma) and by pre-craniotomy phase and post-craniotomy phase. Both absolute concentrations and ratios relative to plasma will be determined for the different sample types, if data permit.

### **2.5.2 Statistical hypothesis, model, and method of analysis**

Not applicable.

### **2.5.3 Handling of missing values/discontinuations**

Missing values for any PK, and tissue concentrations and distribution (when applicable) will not be imputed and will be treated as missing. Below the limit of quantitation (BLQ) values (<1 ng/mL for a 50- $\mu$ L aliquot of human plasma for dabrafenib, hydroxy-dabrafenib and desmethyl-dabrafenib and <5 ng/mL for a 25- $\mu$ L aliquot of human plasma for carboxy-dabrafenib) will be set to zero by the Bioanalyst, and will be displayed in the listings as zero and flagged. BLQ values (<5 ng/g for dabrafenib and hydroxy-dabrafenib and <30 ng/g for desmethyl-dabrafenib for a 50  $\mu$ L aliquot of tissue homogenate) for tissue concentrations and distribution (when applicable) and trametinib (<5 ng/g for a 50  $\mu$ L aliquot of tissue homogenate) (Cohort B only) in the measured tissues (i.e., parenchymal brain metastases, optional assessment of extracranial metastases) will be set to zero by the Bioanalyst.

Concentrations measured in CSF sample below the limit of quantitation (BLQ) values (<1 ng/mL for dabrafenib, hydroxy-dabrafenib and desmethyl-dabrafenib, <5 ng/mL for carboxy-dabrafenib and <0.250 ng/mL for trametinib) will be set to zero by the Bioanalyst, and will be displayed in the listings as zero.

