### **9.2.4.1. Primary Analysis**

#### **9.2.4.1.1. Pharmacokinetics**

Pharmacokinetic analysis will be the responsibility of the Clinical Pharmacology Modeling & Simulation department within GlaxoSmithKline. Levels of dabrafenib, its metabolites, and trametinib (Cohort B only) will be summarized for each tissue (brain metastases, optional assessment of extracranial metastases, and mandatory assessment of plasma for all subjects). Concentrations in plasma will be summarized by nominal times and the average concentrations calculated and summarized. Both absolute concentrations and ratios relative to plasma will be determined for the different sample types. Total and free concentrations may be reported. If necessary, the plasma concentration at time of the surgery or collection may be interpolated.

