**Listing 16.2.5-2.1 PK concentrations for dabrafenib and dabrafenib metabolites plasma (Pharmacokinetic Analysis Set)**

Treatment: xxxxx

Tissue Type: xxxxx

Phase: xxxxxx

Country/ Center/ Subject	Age/ Sex/Race	Analyte	Visit	Sample Collected Time	Assessment Date Time	Concentration (ng/mL)	BLQ Yes/No #
xxx/xxxx/xxxxx	xx/x/xx	Dabrafenib	Day 1	Before Surgery	YYYY-MM-DD hh:mm	xx.xx	
					YYYY-MM-DD hh:mm	xx.xx	
					YYYY-MM-DD hh:mm	xx.xx	
				After Surgery	YYYY-MM-DD hh:mm	xx.xx	
					YYYY-MM-DD hh:mm	xx.xx	
xxx/xxxx/xxxxx	xx/x/xx		Day 1	Before Surgery	YYYY-MM-DD hh:mm	xx.xx	
					YYYY-MM-DD hh:mm	xx.xx	
				After Surgery	YYYY-MM-DD hh:mm	xx.xx	
					YYYY-MM-DD hh:mm	xx.xx	

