# Below the limit of quantitation (BLQ) values (<1 ng/mL for a 50-µL aliquot of human plasma for dabrafenib, hydroxy-dabrafenib and desmethyl-dabrafenib and <5 ng/mL for a 25-µL aliquot of human plasma for carboxy-dabrafenib) have been set to zero and flagged.

BLQ values (<5 ng/g for dabrafenib and hydroxy-dabrafenib and <30 ng/g for desmethyl-dabrafenib for a 50 µL aliquot of tissue homogenate) for tissue concentrations in the measured tissues (i.e., parenchymal brain metastases, optional assessment of extracranial metastases) have been set to zero and flagged.

**Listing 16.2.5-2.2 PK concentrations for dabrafenib and dabrafenib metabolites in cerebrospinal fluid (Pharmacokinetic Analysis Set)**

Treatment: xxxxxx

Tissue Type: xxxxxx

Phase: xxxxxxx

Country/ Center/ Subject	Age/ Sex/Race	Analyte	Visit	Sample Collected Time	Assessment Date Time	Concentration (ng/mL) #	BLQ Yes/No
xxx/xxxx/xxxxx	xx/x/xx	Dabrafenib	Day 1	Before Surgery	YYYY-MM-DD hh:mm	xx.xx	
					YYYY-MM-DD hh:mm	xx.xx	
					YYYY-MM-DD hh:mm	xx.xx	
				After Surgery	YYYY-MM-DD hh:mm	xx.xx	
					YYYY-MM-DD hh:mm	xx.xx	
xxx/xxxx/xxxxx	xx/x/xx	Trametinib	Day 1	Before Surgery	YYYY-MM-DD hh:mm	xx.xx	
					YYYY-MM-DD hh:mm	xx.xx	
				After Surgery	YYYY-MM-DD hh:mm	xx.xx	
					Sample Collected Time	YYYY-MM-DD hh:mm	xx.xx

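### Tissue and CSF values below the assay limit are set to zero before ratios to plasma are formed, so a ratio prints as 0 where only an upper bound is known; the brain listing has no dedicated below-limit mark

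*SAP*

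**What the plan says.** SAP 2.5.3 gives tissue limits of "<5 ng/g for dabrafenib and hydroxy-dabrafenib and <30 ng/g for desmethyl-dabrafenib", and 5 ng/g for trametinib in Cohort B. Tissue results under these limits "in the measured tissues (i.e., parenchymal brain metastases, optional assessment of extracranial metastases) will be set to zero by the Bioanalyst". CSF results under their own limits are also set to zero.

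SAP 2.5.1, on the primary endpoint, then states: "Both absolute concentrations and ratios relative to plasma will be determined for the different sample types, if data permit". SAP 2.7 makes the same provision for CSF. The protocol's primary analysis (9.2.4.1.1) has it without the proviso: "Both absolute concentrations and ratios relative to plasma will be determined for the different sample types".

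SAP 2.5.1 also limits what will be reported: "As a short close-out CSR will be produced, summary analyses will not be performed". Concentrations are to be listed by subject.

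The listing shells treat the matrices differently. The plasma listing (16.2.5-2.1) and the CSF listing (16.2.5-2.2) each have a yes/no BLQ column and a footnote. The brain listing (16.2.5-2.3), in ng/g, has neither; it has a free-text Comment column. A footnote about tissue does exist, saying that BLQ values "for tissue concentrations in the measured tissues (i.e., parenchymal brain metastases, optional assessment of extracranial metastases) have been set to zero and flagged", but it is printed under Listing 16.2.5-2.1, whose title names plasma and whose unit is ng/mL.

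**The concern.** A BLQ result is left-censored: the concentration lies somewhere from zero up to the limit. Replacing it with zero and dividing by plasma turns an upper bound into an exact ratio of 0. The SAP does not say how to form or show a ratio when either term is BLQ, so the zero rule carries through by default.

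The study was set up to learn how much drug reaches brain metastases compared with plasma. With 6 patients and no summary analyses, the individual values, and any ratios formed from them, are what the report will show for the brain part of the primary endpoint. The tissue limits also differ between analytes, so equal zeros in the brain listing would carry different bounds, and that shell shows no limit.

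**Working it through.** **Inputs**
- Tissue limits (SAP 2.5.3): 5 ng/g for dabrafenib, hydroxy-dabrafenib and trametinib; 30 ng/g for desmethyl-dabrafenib.
- CSF limits (SAP 2.5.3): 1 ng/mL for dabrafenib, hydroxy- and desmethyl-dabrafenib; 5 ng/mL for carboxy-dabrafenib; 0.250 ng/mL for trametinib.
- Plasma limits (SAP 2.5.3): 1 ng/mL for dabrafenib, hydroxy- and desmethyl-dabrafenib; 5 ng/mL for carboxy-dabrafenib.
- Plasma concentrations: not given. Assumed values of 10, 100 and 1000 ng/mL show the range; 1 ng/mL is the lowest quantifiable value for the three analytes with that limit.
- Tissue in ng/g is set against plasma in ng/mL by taking 1 g as about 1 mL (assumption).

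The plan states no figure on this point, so there is none to reproduce.

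**Formulas for a BLQ numerator and quantifiable plasma**
- Under the stated rule: ratio = 0 / plasma = 0, for every analyte at every plasma level.
- What the data support: 0 ≤ ratio < LLOQ / plasma, where LLOQ is the limit in the numerator's matrix.

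**Upper bound LLOQ / plasma**

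| Numerator limit | Plasma 1 ng/mL (limit) | 10 | 100 | 1000 |
|---|---|---|---|---|
| Tissue, 5 ng/g (dabrafenib, hydroxy-dabrafenib) | 5/1 = 5 | 0.5 | 0.05 | 0.005 |
| Tissue, 30 ng/g (desmethyl-dabrafenib) | 30/1 = 30 | 3 | 0.3 | 0.03 |
| CSF, 1 ng/mL (dabrafenib, hydroxy-, desmethyl-dabrafenib) | 1/1 = 1 | 0.1 | 0.01 | 0.001 |

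Trametinib in tissue has the same bounds as the first row at the assumed plasma levels, but 2.5.3 states no plasma limit for it, so the 1 ng/mL column does not apply. For carboxy-dabrafenib no tissue limit is stated, so no tissue bound can be computed.

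The tissue bound reaches 1 when plasma is at or below 5 ng/mL (5 ng/g limit) or 30 ng/mL (30 ng/g limit). In that range a ratio of 0 would be compatible with tissue levels close to plasma. The two tissue limits differ by 30/5 = 6-fold.

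**BLQ plasma.** Plasma is also set to zero, so the ratio is x/0, or 0/0 if the numerator is BLQ too. Neither can be computed.

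**Trametinib.** Protocol 5.3 assigns the first 5 enrolled subjects to Cohort A. If that order was followed, 6 − 5 = at most 1 patient is in Cohort B.

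**Shells side by side**

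| Listing | Matrix in title | Unit | BLQ column | Footnote under it |
|---|---|---|---|---|
| 16.2.5-2.1 | Plasma | ng/mL | Yes | Plasma limits, and tissue limits except trametinib |
| 16.2.5-2.2 | CSF | ng/mL | Yes | CSF limits except trametinib |
| 16.2.5-2.3 | Brain metastases | ng/g | No | None |

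Listing 16.2.5-2.1 also carries the header line "Tissue Type: xxxxx". With the footnote, this shows that a tissue flag was intended. The shell that receives the brain values has no dedicated place for it.

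**The case against.** The strongest reply is that no ratio of 0 is actually prescribed. Ratios depend on data permitting, the output contents name no ratio table or listing, and none of the PK shells has a ratio column. A BLQ sample has no quantified numerator, so the proviso could fairly be read as excluding it. On flagging, the footnote already states the intent and prints the 5 and 30 ng/g limits, and the Comment column in the brain listing could carry a remark. Anyone who has read 2.5.3 knows that a zero there means BLQ.

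Much of this stands and keeps the point small. It does not remove it. The proviso plainly covers BLQ plasma, where division fails. It does not clearly cover BLQ tissue or CSF, because 0/plasma can be computed. The Comment column is not assigned to this use, and a reader of the brain listing alone would see neither the rule nor the limit.

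Three stronger readings are tempting, and the documents do not support them:
- **A biased mean or confidence interval.** SAP 3.1 still describes ratio summaries with 95% intervals, but that is the original sample-size rationale. SAP 2.5.1 drops summary analyses and SAP section 4 confirms the change.
- **A report that the drug does not enter the tumor.** Nothing shows that any tissue or CSF value was BLQ, or that a ratio of 0 will be printed.
- **Brain zeros that will certainly print unmarked.** The shell lacks a dedicated column, but the Comment field is available and flagging is the stated intent.

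**Conclusion.** The point holds as a minor one. Applied literally, the zero rule in SAP 2.5.3 combined with the ratios in 2.5.1 and 2.7 gives an exact 0 where the data support only a bound, in brain, extracranial tissue and CSF alike. The brain listing also lacks the BLQ column and footnote that the plasma and CSF listings have.

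The size depends on plasma. The bound is negligible at 1000 ng/mL (0.005 or 0.03 in tissue) and material at 10 ng/mL (0.5 or 3). The values of 5 and 30 at the plasma limit are the extreme case and should not be read as expected: Protocol 3.1.2 says that two dabrafenib metabolites accumulate with repeat dosing and that desmethyl-dabrafenib should be fairly constant during surgery. All of these figures rest on assumed plasma levels or the stated limits, and the tissue figures also take 1 g as about 1 mL.

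The effect is confined to individual listed values, and any ratios, in 6 patients.

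**What to change.** 1. In SAP 2.5.3, state that a ratio with a BLQ numerator (brain, extracranial tissue or CSF) is reported as <(LLOQ/plasma), and that a ratio with BLQ plasma is reported as not calculable.
2. In Listing 16.2.5-2.3, add a BLQ column that shows the numeric limit, and place the tissue footnote there, including the 5 ng/g trametinib limit from 2.5.3.
3. While editing, state the tissue limit for carboxy-dabrafenib and the plasma limit for trametinib, or say that they were not assayed.

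The CSF listing already has its BLQ column; CSF needs only the ratio sentence in step 1. The cost is a short edit to 2.5.3 and one shell, with no new samples or analyses. The downside is that some ratios become upper bounds instead of point values.

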## **2.6 Analysis of the key secondary objective**

Not applicable.

## **2.7 Analysis of secondary objective(s)**

As a short close-out CSR will be produced, analyses will not be performed for secondary endpoints. The concentration of dabrafenib, dabrafenib metabolites and trametinib (Cohort B only) in CSF will be listed for each cohort by pre-craniotomy phase and post-craniotomy phase. Both absolute concentrations and ratios relative to plasma will be determined for the different sample types, if data permit.

## **2.8 Safety analyses**

All safety analyses will be based on the safety set. Summaries will be sorted and displayed by cohorts.

### **2.8.1 Adverse events (AEs)**

AE summaries will include all AEs occurring during on treatment period. All AEs collected in the AE (e)CRF page will be listed along with the information collected on those AEs e.g. AE relationship to study drug, AE outcome etc. AEs with start date outside of on-treatment period will be flagged in the listings.

AEs will be summarized by number and percentage of subjects having at least one AE, having at least one AE in each primary system organ class (SOC) and for each preferred term (PT) using MedDRA coding. A subject with multiple occurrences of an AE will be counted only once in the respective AE category. A subject with multiple CTCAE grades for the same preferred term will be summarized under the maximum CTCAE grade recorded for the event.

In AE summaries, the primary system organ class (SOC) will be presented alphabetically and the preferred terms will be sorted within primary SOC in descending frequency. The sort order for the preferred term will be based on their frequency.

The following AE summaries will be produced: AEs by SOC, PT and maximum grade, summarized by relationship to study drug, seriousness, leading to treatment discontinuation, in addition, a summary of serious adverse events with number of occurrences will be produced.

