## **Objective(s)**

The primary objective of this study is to determine levels and distribution of dabrafenib, its metabolites, and trametinib (Cohort B only) in parenchymal brain metastases, extracranial metastases (when available), and peripheral blood (plasma) within two cohorts of subjects with BRAF V600E/K mutation-positive melanoma that has metastasized to the brain.

The secondary objectives of this study are to determine: the levels of dabrafenib, its metabolites, and trametinib (as appropriate) in the cerebrospinal fluid (CSF) and in extracranial metastases where possible; the activation status of the RAS-RAF-MEK-ERK signalling pathway in brain metastases and extracranial metastases; the activation status of other pro-survival signalling pathways in brain metastases and extracranial metastases; the relationship between these pharmacokinetic and pharmacodynamic measures and early clinical responsiveness of the brain metastases; the degree of concordance with respect to the presence of BRAF mutations in both the brain and extra-cranial metastases from the same subjects, the presence of other mutations that may be uniquely present and novel only for brain metastases; and the safety and tolerability of pre-operative treatment with dabrafenib or dabrafenib combined with trametinib prior to resection of brain metastases, as well as the surgical outcomes from the craniotomy itself. Efficacy will be assessed in terms of change from baseline to pre-surgery in the sum of the longest diameters of intracranial target lesions, maximum change from baseline in the sum of longest diameters of unresected intracranial target lesions, overall extracranial response rate in unresected lesions, and overall survival.

The exploratory objectives of this study are to determine, in available samples, the degree of concordance with respect to the presence of BRAF mutations in both the brain and extra-cranial metastases from the same subjects; the presence of other mutations that may be uniquely present and novel only for brain metastases; and to compare the status of signalling pathways and the immune response in brain metastases and extra-cranial metastases.

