of the brain and whole-body PET-CT imaging will also be performed between 1 to 3 days prior to surgery. On the day of surgery, blood samples will be collected for pharmacokinetic analysis. Two samples will be collected prior to surgery, and two samples will be collected after surgery; all samples will be separated in time by at least 1 hour. Optional collection of CSF will be obtained in the operating room on the day of brain metastasis resection; this procedure is described in Section 6.5 of the protocol. Portions of the resected brain metastasis(es) that in the clinical judgment of the neurosurgeon performing the operation are not required to be submitted for pathological confirmation of melanoma brain metastasis will be divided into sections to be used for pharmacokinetic, pharmacodynamic, and exploratory translational research studies. Optional collection of an easily accessible extracranial metastasis may be performed after the PET-CT scan and up to 1 day after the removal of brain metastasis(es); which will be similarly divided for studies. The time of collection of brain metastasis, the plasma samples, and the optional extracranial metastasis(es) and CSF will be recorded for the purpose of the pharmacokinetic analysis, as well as the time the last dose of study treatment was taken.

Subjects in either cohort with intracranial and/or extracranial metastases remaining after surgery may resume treatment with the combination of dabrafenib 150 mg BID and trametinib 2 mg once daily no earlier than 72 hours after surgery at the discretion of the Principal Investigator. Subjects continuing on treatment will be evaluated for safety 4 weeks after restarting treatment, and every 4 weeks thereafter. These subjects will be evaluated for efficacy eight weeks after restarting treatment, and every 8 weeks thereafter.

[figure not shown]
Subjects who do not continue treatment after the craniotomy procedure will be evaluated for safety at the discontinuation visit 4 weeks after the craniotomy.

All subjects who permanently discontinue study treatment will be followed for survival and new anti-cancer therapy for a total of two years or until death or the subject wishes to withdraw from further follow-up. The study will be considered closed once the last subject reaches this milestone.

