#### **4.2. Permanent Discontinuation from Study Treatment and Subject Completion Criteria**

All subjects will receive study treatment until the day prior to the resection of their brain metastasis (es), or until unacceptable adverse event, including meeting stopping criteria for hematologic and other non-hematologic toxicity. Subjects who have additional melanoma metastases after resection of their brain metastasis (es) and optional sampling of easily accessible extracranial metastases may resume treatment with the combination of dabrafenib 150 mg BID and trametinib 2 mg once daily no earlier than 72 hours after completion of their surgical procedures, at the discretion of the treating physician.

Subjects will be permitted to receive the combination of dabrafenib 150 mg BID and trametinib 2 mg once daily until disease progression, death, or unacceptable AE, including hematologic or other non-hematologic toxicity, and/or meeting stopping criteria for liver chemistry defined in Section 5.7.6. In addition, study treatment may be permanently discontinued at any time for any of the following additional reasons:

- deviation(s) from the protocol
- request of the subject or proxy
- investigator's discretion
- subject is lost to follow-up

- study is terminated.

The primary reason that study treatment was permanently discontinued must be documented in the subject's medical records and eCRF.

If the subject voluntarily discontinues from treatment due to toxicity, 'adverse event' will be recorded as the primary reason for permanent discontinuation on the eCRF.

Once a subject has permanently discontinued from study treatment, the subject will not be allowed to be retreated.

All subjects who discontinue from study treatment will have safety assessments at the time of discontinuation and follow-up as specified in Time and Events Table (Table 19) and Section 7.11.

All subjects will be followed for survival and new anti-cancer therapy for a total of two years or until the subject wishes to withdraw from further follow-up.

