#### **Treatment**

For presentation in the outputs, treatment refers to

Cohort A : Dabrafenib prior to surgery

Cohort B : Dabrafenib + Trametinib prior to surgery

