### **On-treatment assessment/event and observation periods**

The overall observation period will be divided into three mutually exclusive segments:

**Pre-treatment period** is defined as from day of patient's informed consent to the day before first administration of study treatment

**On-treatment period** is defined as from date of first administration of study treatment to 30 days after date of last actual administration of study treatment (including start and stop date)

**Post-treatment period** is defined as starting at day 30+1 after last administration of study treatment.

Notes: if data on clock time is available in the clinical database (e.g. for time of blood/urine sample taken, ECG performed, etc. and first study treatment administration), a more precise distinction between pre-treatment and on-treatment periods is encouraged to be used. If dates are incomplete in a way that clear assignment to pre-, on-, post-treatment period cannot be made, then the respective data will be assigned to the on-treatment period.

Safety summaries (tables, figures) include data from the pre-treatment period (to display the baseline status e.g. for ECG) and the on-treatment period, i.e. data from the post-treatment period with the exception of deaths should not be included unless requested from Health Authorities or external committees.

In particular, summary tables for adverse events (AEs) will summarize only on-treatment events, with a start date during the on-treatment period, the so-called *treatment-emergent* AEs.

However, all safety data (including those from the post-treatment period) will be listed and those collected during the pre-treatment and post-treatment period are to be flagged.

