### **1.3 Treatment group labels and ordering**

The following treatment labels will be used for all tables, listings and figures in the order provided here:

- Treatment group label 1  
Cohort A Cohort B All subjects

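### Exposure shells lack the pre-/post-craniotomy split that SAP 2.4.1 requires, and AE tables pool all phases under a Cohort A label that names only the pre-surgery regimen

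*SAP*

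**What the plan says.** **Exposure.** SAP 2.4.1 (Study treatment / compliance) commits to summarising dose administration by cohort and by phase, before and after craniotomy, on the Safety Set. Its next paragraph defines one duration of exposure, from first dose to the later of the two drugs' last doses. Shell Table 14.3-1.1 shows that duration for Cohort A, Cohort B and all subjects. Shell Table 14.3-1.2 shows duration and cumulative dose for dabrafenib and trametinib, without cohort. Neither has a phase.

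**Adverse events.** SAP 2.8.1: "AE summaries will include all AEs occurring during on treatment period". The on-treatment period (SAP 2.1.1) "is defined as from date of first administration of study treatment to 30 days after date of last actual administration of study treatment". SAP 2.8 adds: "Summaries will be sorted and displayed by cohorts". The output label is "Cohort A : Dabrafenib prior to surgery", and Section 1.3 of the shells allows only the columns "Cohort A Cohort B All subjects". A subject counts once per term, at maximum grade.

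**Treatment after surgery.** Under Protocol Section 3, subjects of either cohort who still have metastases once the operation is done "may resume treatment with the combination of dabrafenib 150 mg BID and trametinib 2 mg once daily no earlier than 72 hours after surgery". Under Protocol 4.2 this treatment may run "until disease progression, death, or unacceptable AE".

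**Safety question.** The Protocol Summary lists among its objectives "the safety and tolerability of pre-operative treatment with dabrafenib or dabrafenib combined with trametinib prior to resection of brain metastases", together with the surgical outcomes of the craniotomy. Protocol 3.1 also names safety of preoperative treatment.

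**The concern.** Two things look wrong.

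- The SAP text promises a phase split of dosing data that its own table shells cannot deliver. A programmer working from the shells would produce tables that do not meet SAP 2.4.1.
- A Cohort A subject who restarts changes regimen inside one AE window, while the column heading names only the first regimen. A reader who takes that column as the safety of pre-operative dabrafenib would also be counting perioperative events and events that began on dabrafenib plus trametinib. No planned AE table isolates the pre-operative safety that the Protocol Summary and Protocol 3.1 name.

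**Working it through.** The plan states no figure on this point, so the main check sets the passages side by side. The arithmetic only sizes the effect.

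**1. Exposure: text against shells.**
- SAP 2.4.1 requires cohort × phase. Table 14.3-1.1 gives cohort only, and Table 14.3-1.2 gives compound only. No other dose or exposure summary shell exists, and in-text Table 12-1 reuses 14.3-1.1.
- SAP Section 4 lists the changes from protocol-specified analyses and does not mention dropping the split.
- The single duration does not satisfy the requirement, because it runs across the surgical break. For example, 7 pre-operative days, a 3-day gap and an assumed 28 days after restart give 7 + 3 + 28 = 38 days of exposure against 7 + 28 = 35 dosed days, with no indication of how many came before surgery.

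**2. Adverse events: what one Cohort A column holds.** The window is continuous, the display is by cohort, the cohort is defined by the pre-surgery regimen, and restart is on the combination. Pre-operative, surgical-recovery and post-restart events of a resumer therefore share one column. None of the AE table shells (in-text 12-2 to 12-9; 14.3.1-1.1 to 14.3.1-1.10) has a phase or regimen split. Cohort B restarts on the same two drugs, so regimens are mixed for Cohort A only.

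**3. Effect on one table cell.**
- Inputs: 6 subjects enrolled (SAP 3.1). No cohort split is given. The order in Protocol 5.3 would give 5 in Cohort A and 1 in Cohort B. A 6/0 split is possible if a Cohort A subject was replaced or if subjects enrolled under an earlier assignment sequence. Both splits are assumptions.
- One subject is 1/5 = 20.0 or 1/6 = 16.7 percentage points.
- Condition: a post-restart event adds to a cell only if that subject had no earlier event of the term or, for the Grade ≥3 column, none at that grade.
- Maximum grade: the main and overview shells show All grades and Grade ≥3 only. A subject with an earlier grade 1 or 2 event stays in All grades whatever follows. The display changes only if the later event reaches grade 3 or higher.

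**4. Share of the AE window, as illustration only.**
- d = pre-operative dosing days, 7 or 14 (Protocol Section 3). g = days from surgery to restart, 3 (the 72-hour minimum) or 14 (assumed). T = total exposure as the SAP defines it, taken at boundaries of Table 14.3-1.1. Window W = T + 30.
- Post-restart share = (W − d − g)/W. Pre-operative share = d/W.

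| T | W | Post-restart share | Pre-operative share |
|---|---|---|---|
| 4 weeks (28 days), d = 7 | 58 | 37/58 = 63.8% (g = 14) to 48/58 = 82.8% (g = 3) | 7/58 = 12.1% |
| 8 weeks (56 days) | 86 | 58/86 = 67.4% to 76/86 = 88.4% | 8.1% to 16.3% |
| 12 weeks (84 days) | 114 | 86/114 = 75.4% to 104/114 = 91.2% | 6.1% to 12.3% |
| 60 weeks (420 days) | 450 | 422/450 = 93.8% to 440/450 = 97.8% | 1.6% to 3.1% |

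At 4 weeks, d = 14 with g = 14 would leave no days on treatment after restart, so that row uses d = 7. For a subject who does not resume, the window is d + 30 days, of which 7/37 = 18.9% to 14/44 = 31.8% is on dabrafenib. The rest is surgery and recovery. All of these are shares of time, not of events.

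**5. Partial AE dates, if a phase split is added.** Rule (B) in SAP Table 5-3 sets an uncertain start date to treatment start + 1, which is study day 2. With at least 7 dosing days, surgery is on day 8 or later. Rule (B) would therefore always place such an event before surgery.

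**The case against.** **The pooled AE window follows the protocol.** Protocol 7.3 defines the safety endpoint over treatment with dabrafenib or the combination. Protocol 7.3.1.5 uses one collection window to 30 days after discontinuation. Protocol Table 1 words the safety objective broadly, and Protocol 9.2.4.3.2 plans no phase split. This stands. A reader might infer that the SAP departs from the protocol on AEs, and it does not.

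**The harm is limited.** No cohort comparison is planned (Protocol Section 2), and the label does say that its regimen is the pre-surgery one. With 6 subjects, onset can be matched by hand: Listing 16.2.7-1.1 gives AE start dates and study days, Listing 16.2.5-1.1 gives dosing dates, and action code X marks some off-drug events. This also stands, although surgery date is not a field in either listing.

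**Mixing may not have occurred.** The number of resumers is not given. The protocol's revision chronology shows that Amendment 1 changed post-operative treatment to the combination, so a subject treated before it may not have restarted on both drugs. This stands as a limit on size.

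**The phase sentence concerns dose administration, and Table 14.3-1.1 matches the duration paragraph.** Both are true, but no other shell meets the phase requirement. The shells are not wholly uninformative. Under the current protocol, Cohort A receives trametinib only after surgery, so the trametinib column of 14.3-1.2 is all post-surgery exposure if the split is 6/0 and may be largely so if it is 5/1. That is not the summary promised in SAP 2.4.1.

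**Conclusion.** The concern holds in two parts of different standing. Overall severity is minor.

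- **Exposure: wrong as written.** SAP 2.4.1 and shells 14.3-1.1 and 14.3-1.2 disagree, and Section 4 does not explain it. This holds however many subjects resumed.
- **Adverse events: a cheap improvement.** The tables cannot isolate pre-operative safety. For any Cohort A subject who restarted on dabrafenib plus trametinib, they mix regimens under a pre-surgery label. The size is 16.7 to 20.0 points per affected cell, on the assumed 6 or 5 subjects and the no-earlier-event condition above. It applies to 0 to 5 or 6 resumers.

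Two stronger readings are not supported. The large post-restart time shares might suggest that most Cohort A events arose on the combination, but the documents give neither actual durations nor resumer numbers, and time is not event count. Counting at maximum grade might suggest that pre-operative events disappear. They remain in the listings and in All grades, and their display changes only when a later event reaches grade 3 or higher.

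**What to change.** 1. Add cohort and pre-/post-craniotomy phase to Tables 14.3-1.1 and 14.3-1.2, and to in-text Table 12-1, so that they match SAP 2.4.1.
2. In Listings 16.2.7-1.1 and 14.3.2-1.2, add a flag for phase at onset (pre-craniotomy; surgery to restart; after restart) and the actual regimen at onset, taken from the dosing record and not assumed from the cohort.
3. Show the AE overview (14.3.1-1.10) and the main AE table (14.3.1-1.1) by cohort and phase beside the planned pooled column. Use as denominator the subjects who entered each phase, and assign each AE by its recorded start date. Footnote that onset phase does not establish causality, since delayed toxicity of pre-operative drug can begin after surgery or restart.
4. Where a partial start date does not determine the phase, label the AE as phase uncertain and do not let rule (B) place it. No partial date is known to exist.

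The cost is short SAP text, flags in two listings, four re-cut tables, and updates to the in-text tables that draw on them (12-1 to 12-4), all for 6 subjects and mainly from dates already collected. The downsides are small cells, a few extra outputs, and some risk that onset phase is read as cause, which the footnote and the pooled column are there to limit.
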